### **Chest X-Ray (CXR)**

A CXR (posterior-anterior and lateral views) is required:

- For all subjects at Screening to rule out the presence of TB or other clinically relevant findings. The CXR will not be required if the subject had a previous normal CXR (posterior-anterior and lateral views) within 90 days of Screening, provided all source documentation is available at the site as outlined below and provided nothing has changed in the subject's medical history to warrant a repeat test.
- Every 48 weeks for subjects with TB risk factors as identified by the TB risk assessment form ([Appendix E](#)), or for subjects living in areas endemic for TB or for subjects with newly positive PPD and/or QuantiFERON®-TB Gold test.

Subjects can have a repeat CXR at any time during the study as warranted, based on the opinion of the Investigator.

A radiologist, internist or pulmonologist must perform an assessment of the CXR. The Investigator will indicate the clinical significance of any findings and will sign and date the report. In the assessment of the CXR, the Investigator or their delegate must indicate the presence or absence of (1) calcified granulomas, (2) pleural scarring/thickening, and (3) signs of active TB. If the CXR demonstrates changes suggestive of previous TB (e.g., calcified nodule, fibrotic scar, apical or basilar pleural thickening) or other findings that are clinically significant, the Principal Investigator should contact the AbbVie TA MD before enrolling the subject.

### **12-Lead ECG**

A resting 12-lead ECG will be performed at the designated study visits as specified in [Table 2](#) and [Table 4](#). A qualified physician will interpret the clinical significance of any abnormal finding, sign, and date each ECG. ECG with QT interval corrected for heart rate using Friedericia's correction formula (QTcF) should be reported (or calculated) and documented in the source documents and later transcribed on to the appropriate eCRF if QTcF prolongation is observed. A valid QTcF cannot be calculated in subjects who have a pacemaker or supraventricular or ventricular conduction abnormalities. In case of QTcF prolongation, the baseline QTcF will need to be entered into the appropriate eCRF for comparison as well. In addition, any clinically significant findings will be documented in

the source documents and later transcribed on to the appropriate eCRF. Each signed original ECG will be monitored by the responsible site monitor and kept with subject's source documents onsite.

For subjects with a normal ECG taken within 90 days of Screening, a repeat ECG at Screening will not be required, provided source documentation is available and provided nothing has changed in the subject's medical history to warrant a repeat test. If there are other findings that are clinically significant, the Investigator must contact the AbbVie TA MD before enrolling the subject.

Subjects can have a repeat ECG at any time during the study as warranted based on the opinion of the Investigator.

### **Height and Weight**

Height will be measured at the Screening Visit only (with shoes off). Body weight will be measured at all scheduled visits except Week 1 as specified in [Table 2](#) and [Table 4](#). All measurements will be recorded in metric units where applicable.

### **Vital Signs**

Vital sign determinations of systolic and diastolic blood pressure in sitting position, pulse rate, respiratory rate, and body temperature will be obtained at visits specified in [Table 2](#) and [Table 4](#). Blood pressure, pulse rate, body temperature, and respiratory rate should be performed before blood draws are performed.

### **Physical Examination**

A complete physical examination will be performed at the designated study visits as specified in [Table 2](#) and [Table 4](#). The physical examination at the Baseline Visit will serve as the baseline physical examination for the entire study. Physical examination abnormalities noted by the Investigator at Baseline prior to the first dose of study drug will be recorded in the subject's medical history; abnormalities noted after the first dose of study drug will be evaluated and documented by the Investigator as to whether or not the

abnormality is an AE (see Section 6.1.1.1 for AE definition). All findings, whether related to an AE or part of each subject's medical history, will be captured on the appropriate eCRF page.

At any time, a symptom-directed physical examination can be performed as deemed necessary by the Investigator.

### **Physician's Global Assessment of Disease Activity VAS**

At visits specified in [Table 2](#) and [Table 4](#), the Physician will rate global assessment of subject's current disease activity ranging from 0 to 100 independent of the subject's self-assessment using the VAS, which consists of a horizontal 100 mm line anchored at either end by opposite adjectives reflecting the spectrum/severity of the parameters assessed ([Appendix C](#)).

### **TJC and SJC Assessment**

#### *TJC Assessment*

An assessment of 68 joints ([Appendix D](#)) will be done for tenderness by pressure manipulation on physical examination at visits specified in [Table 2](#) and [Table 4](#). Joint pain/tenderness will be classified as: present ("1"), absent ("0"), replaced ("9") or no assessment ("NA").

#### *SJC Assessment*

An assessment of 66 joints ([Appendix D](#)) will be done by directed physical examination at visits specified in [Table 2](#) and [Table 4](#). The joints to be examined for swelling are the same as those examined for tenderness, except the hip joints are excluded. Joint swelling will be classified as present ("1"), absent ("0"), replaced ("9") or no assessment ("NA").

Any injected joints will be considered as "not assessed" ("NA") for 3 months from the time of the intra-articular injection.

If possible, the TJC and SJC should be performed by an independent and blinded joint assessor who should not perform any other study related procedures.

In order to minimize variability, the same independent joint assessor should evaluate the subject at each visit for the duration of the trial as much as possible. A back-up independent joint assessor should be identified. The independent joint assessor should be a qualified medical professional (e.g., nurse, physician's assistant, physician). Any other joint assessor must be trained and competent in performing such assessments. It is the responsibility of the Investigator to ensure that all assessors are qualified and trained to perform joint assessments. If the independent assessor is not available, the pre-identified back-up assessor should perform such assessments.

### **CDAI**

The CDAI calculation is required to determine if a subject fails to achieve low disease activity at the Week 24 visit. An Interactive Response Technology (IRT) will calculate CDAI with input from site personnel on joint counts and the subject's and physician's Global Assessment of RA Disease Activity score. A worksheet will be provided to capture the components required for IRT entry to obtain the CDAI calculation.

The calculation used to determine CDAI score at Week 24 is as follows:

$$\text{CDAI} = \text{TJC28} + \text{SJC28} + \text{PtGA} + \text{PhGA}$$

NOTE: Investigator should optimize background RA therapies in subjects who failed to achieve a CDAI  $\leq 10$ .

### **Pregnancy Test**

A serum pregnancy test will be performed for all women of childbearing potential at the Screening Visit. Women of non-childbearing potential (either postmenopausal or permanently surgically sterile as defined above) at Screening do not require pregnancy testing. The serum pregnancy test will be sent to and performed by the central laboratory. If the serum pregnancy test is positive the subject is considered a screen failure. If the

serum pregnancy test is borderline, it should be repeated  $\geq 3$  days later to determine eligibility. If the repeat serum pregnancy test is:

- Positive, the subject is considered a screen failure;
- Negative, the subject can be enrolled into the trial;
- Still borderline, this will be considered documentation of continued lack of a positive result and the subject can be enrolled into the trial.

In Period 1, a urine pregnancy test will be performed for all women of child bearing potential at the Baseline Visit prior to the first dose of study drug and all subsequent visits except Week 1. More frequent pregnancy tests will be performed throughout the study if required per local/country requirements.

- If the baseline urine pregnancy test performed at the site is negative, then dosing with study drug may begin. If the baseline urine pregnancy test performed at the site is positive, dosing with study drug must be withheld and a serum pregnancy test is required. The serum pregnancy test will be sent to and performed by the central laboratory. If the serum pregnancy test is positive, study drug must be withheld and the subject must be discontinued from the study. In the event a pregnancy test comes back borderline, a repeat test is required.
- If a urine pregnancy test post-baseline is positive, study drug needs to be temporarily discontinued and a serum pregnancy test is required. The serum pregnancy test will be sent to and performed by the central laboratory. If the serum pregnancy test is negative, study drug may be resumed. If the serum pregnancy test is positive, study drug must be permanently discontinued. In the event a serum pregnancy test comes back borderline, a repeat test is required ( $\geq 3$  days later) to document continued lack of a positive result.

In Period 2 starting at Week 24, for women of childbearing potential, a urine pregnancy test will be performed at all visits and monthly at home between scheduled study visits. The results of the monthly at home tests will be communicated to the site. If a urine

pregnancy test is positive, the subject must stop dosing, come in to the clinic and have blood drawn for a serum pregnancy test that will be analyzed at the central laboratory.

At each visit, the study staff should review the pregnancy avoidance recommendations with women of childbearing potential and male subjects with a partner of childbearing potential, and document this discussion in the subject's source records.

If during the course of the study a woman becomes surgically sterile or post-menopausal and complete documentation as described in Section 5.2.4 is available, pregnancy testing is no longer required.

A pregnant or breastfeeding female will not be eligible for participation or continuation in this study.

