### **Period 2 (Blinded Long-Term Extension Period [up to Regulatory Approval of the RA Indication in Japan])**

Period 2 will begin at the Week 12 visit after all assessments have been completed. During Period 2, subjects will have a study visit at Weeks 16, 20, 24, 36, 48, and every

12 weeks thereafter until completion of the study. A  $\pm$  7 day window is permitted around scheduled study visits. At Week 24, if a subject fails to meet LDA criterion (LDA defined as CDAI  $\leq$  10) investigator should adjust the subject's background RA therapies. Starting at Week 24 and thereafter, at least 20% improvement in BOTH TJC AND SJC compared to baseline is required to remain in the study drug. Anyone who does not fulfill this criterion at 2 consecutive visits (starting at Week 24), despite optimization of background RA therapies (see Section 5.2.3.2) must be discontinued from the study.

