### **Rationale for Inclusion Criteria**

- 1 – 9              To select the appropriate subject population
- 10 – 13            Upadacitinib is teratogenic in both rats and rabbits. The effect of upadacitinib on pregnancy and reproduction is unknown
- 14                  In accordance with harmonized Good Clinical Practice (GCP)

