  - l. For women of childbearing potential, a urine pregnancy test will be performed at all visits and monthly at home between scheduled study visits. Pregnant subjects must discontinue from the study. Refer to Section 5.3.1.1 Study Procedures Pregnancy Test for additional details. If during the course of the study a woman becomes surgically sterile or post-menopausal and complete documentation is available, urine pregnancy test is no longer required.
  - m. Starting at Week 24, for women of childbearing potential, in-home urine pregnancy tests will be performed monthly. The results of the monthly at home tests will be communicated to the site. If a urine pregnancy test is positive, the subject must stop dosing, come in to the clinic and have blood drawn for a serum pregnancy test that will be analyzed at the central laboratory. If during the course of the study a woman becomes surgically sterile or post-menopausal and complete documentation is available, urine pregnancy test is no longer required.

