- l. A urine pregnancy test will be performed for all women of childbearing potential at the Baseline Visit prior to the first dose of study drug and all subsequent visits except Week 1. In Period 2, for women of childbearing potential, a urine pregnancy test will be performed at all visits, including the 30 days follow-up visit, and starting at Week 24 a urine pregnancy test will be performed monthly at home between scheduled study visits. If the baseline urine pregnancy test performed at the site is negative, then dosing with study drug may begin. If the baseline or post-baseline urine pregnancy test performed at the site is positive, dosing with study drug must be withheld and a serum pregnancy test is required. The serum pregnancy test will be sent to and performed by the central laboratory. If the serum pregnancy test is negative, study drug may be started or resumed. If the serum pregnancy test is positive, study drug must be withheld and the subject must be discontinued from the study. In the event a pregnancy test comes back borderline, a repeat test is required ( $\geq 3$  days later) to document continued lack of a positive result. If during the course of the study a woman becomes surgically sterile or post-menopausal and complete documentation as described in Section 5.2.4 is available, pregnancy testing is no longer required.

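### Protocol Section 5.3.1.1 starts all Period 2 urine pregnancy testing at Week 24, while the notes to Tables 4 and 5 call for clinic tests at every Period 2 visit, so Weeks 16 and 20 are tested under one text and unscheduled under the other

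*Protocol*

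**What the plan says.** The protocol sets out Period 2 urine pregnancy testing for women of childbearing potential in three places.

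- Section 5.3.1.1, Pregnancy Test: "In Period 2 starting at Week 24, for women of childbearing potential, a urine pregnancy test will be performed at all visits". The same sentence continues to monthly home tests, so the Week 24 start stands in front of both kinds of test.
- Table 5, note l: "In Period 2, for women of childbearing potential, a urine pregnancy test will be performed at all visits, including the 30 days follow-up visit". The note then turns to home testing: "starting at Week 24 a urine pregnancy test will be performed monthly at home between scheduled study visits".
- Table 4, note l: "For women of childbearing potential, a urine pregnancy test will be performed at all visits and monthly at home between scheduled study visits". Note m gives the start of the home tests: "Starting at Week 24, for women of childbearing potential, in-home urine pregnancy tests will be performed monthly". Notes l and m to Table 3 of the SAP repeat this wording.

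The Period 2 visit schedule in Section 5.1 includes two visits before Week 24: "During Period 2, subjects will have a study visit at Weeks 16, 20, 24, 36, 48".

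On the hazard, the rationale for the inclusion criteria says "Upadacitinib is teratogenic in both rats and rabbits" and adds that the effect on pregnancy and reproduction is not known.

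**The concern.** A site that follows Section 5.3.1.1 as worded has no scheduled pregnancy test at Weeks 16 and 20. A site that follows Table 4 or Table 5 tests at both. Table 4 note l sends its reader to the Pregnancy Test text in Section 5.3.1.1 for further detail, so a site that starts from the table is led to the sentence that disagrees with it. No passage says which text takes precedence.

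The test has consequences. In Period 2 a positive urine result means that the subject stops dosing and comes in for a serum test, and Section 5.4.1 withdraws a subject who becomes pregnant on study drug. Weeks 12 to 24 are also the first 12 weeks on upadacitinib for everyone switched from placebo at Week 12. Beyond detection, a monitor cannot tell whether a missing Week 16 or Week 20 test is a missed procedure or correct conduct.

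**Working it through.** No sample size, power or error-rate figure is involved. The check is a comparison of texts and a count of weeks.

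**Step 1. What each text schedules**

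| Source | Clinic tests in Period 2 | Home tests | Weeks 16 and 20 |
|---|---|---|---|
| Section 5.3.1.1, Pregnancy Test | From Week 24 | From Week 24 | Not scheduled |
| Table 5 note l | All visits, including 30-day follow-up | From Week 24 | Scheduled |
| Table 4 notes l and m, read together | All visits | From Week 24 | Scheduled |
| SAP Table 3 notes l and m | As protocol Table 4 | As protocol Table 4 | Scheduled |

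All four agree on home tests. The disagreement is confined to the first clinic test in Period 2.

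**Step 2. Does another sentence in Section 5.3.1.1 fill the gap?**

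The paragraph before the Period 2 sentence requires tests at visits after Baseline other than Week 1, but it is limited to the first period: "In Period 1, a urine pregnancy test will be performed for all women of child bearing potential at the Baseline Visit". It reaches Week 12 and no further. It also provides for more frequent tests, but only where local or country requirements call for them. Neither provision schedules a test at Week 16 or Week 20.

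**Step 3. Interval between scheduled tests**

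The last Period 1 test is at Week 12 (Table 2 note n). Nominal weeks, before visit windows:

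- Section 5.3.1.1, read literally: Week 24 − Week 12 = 12 weeks.
- Tables 4 and 5: 16 − 12 = 4, 20 − 16 = 4 and 24 − 20 = 4, so 4 weeks each time.

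Two scheduled visits per woman of childbearing potential are affected.

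**Step 4. What could not be used**

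The row of visit marks for the local urine test in Table 4 is damaged in the text available for this review. The comparison rests on the notes, which are sufficient.

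**The case against.** The strongest reply is that this is one misplaced phrase. Table 4, Table 5 and the SAP copy all describe the same split, and only one sentence in Section 5.3.1.1 departs from it. That section introduces itself as discussing the procedures outlined in Tables 2 and 4, and Table 5 note l opens with a rule covering all visits after Baseline except Week 1, without limiting it to Period 1. A drafting slip is therefore a plausible explanation. It does not remove the conflict, because the sentence is current text, sites are referred to it, and nothing ranks it below the tables.

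The reply is right on several further points, each of which limits what a reader might infer:

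- **That a site following Section 5.3.1.1 must omit the tests.** The section leaves Weeks 16 and 20 unscheduled but does not forbid or waive a test there. A site that tests at both visits breaches nothing.
- **That Table 4 notes l and m conflict with each other.** Note l mentions monthly home tests without a start week, and note m supplies it. They can be read together.
- **That testing at the 30-day visit is left open.** Table 5 note l includes it expressly.
- **That the protocol declares the drug teratogenic in humans.** It says so of rats and rabbits only and calls the effect on pregnancy and reproduction unknown.
- **That the 3 × 16 = 48 planned placebo subjects measure the number at risk.** The documents do not say how many of them, or of all subjects, are women of childbearing potential.

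There are also safeguards. Contraception is required from Study Day 1 through at least 30 days after the last dose, staff review pregnancy avoidance at each visit, and a test is done at Week 12. These lower the chance of an exposed pregnancy, but neither contraception nor counselling detects one, and the Week 12 test says nothing about conception after it.

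**Conclusion.** The inconsistency is real and stands in current text. Section 5.3.1.1 attaches the Week 24 start to clinic and home tests alike, while Table 5 note l and Table 4 notes l and m attach it to home tests only. Its size is two scheduled visits, Weeks 16 and 20, and a nominal interval of 12 weeks against 4. The 12-week figure assumes that the sentence is read literally and that no local requirement or investigator decision adds a test.

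The point concerns the conduct of safety monitoring. It is an internal inconsistency rather than a questionable design choice, and it alters no endpoint, analysis set or sample-size quantity. It should be corrected because the rule leads directly to stopping study drug. The documents do not support a claim that pregnancies will go undetected: that would require a site to disregard both tables and no pregnancy to be recognised by other means.

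**What to change.** The sponsor should reconcile the Pregnancy Test text in Section 5.3.1.1 with Table 4 notes l and m and Table 5 note l, so that all three give the same first week for clinic tests and the same first week for home tests in Period 2. The two start weeks should be stated separately, since it is their merging in one clause that causes the conflict. A clarification to sites should go out in the meantime and should say how Week 16 and Week 20 visits already completed are to be judged. The choice of schedule is for the sponsor. The cost is one administrative change and a site memo, and no analysis is affected.

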### **Clinical Laboratory Tests**

Samples will be obtained for the clinical laboratory tests listed in [Table 5](#). Unscheduled clinical labs may be obtained at any time during the study if deemed appropriate per Investigator's discretion. A certified central laboratory will be utilized to process and provide results for the clinical laboratory tests. In cases where laboratory tests are performed locally for specific study purposes, certifications and laboratory reference ranges will be collected for the tests which are performed. All abnormal laboratory tests that are considered clinically significant by the Investigator will be followed to a satisfactory resolution.

The central laboratory chosen for this study will provide instructions regarding the collection, processing, and shipping of these samples.

Blood samples will be obtained for the laboratory tests at visits specified in [Table 2](#) and [Table 4](#). Blood draws should be performed only after all clinical assessments and questionnaires (HAQ-DI, Patient's Assessment of Pain, etc.) and vital sign determinations are obtained.

For clinic visits where samples for serum chemistry tests are collected, subjects should be fasting (a minimum 8-hour fast) whenever possible. If a subject is not able to fast when necessary, due to unforeseen circumstances, the non-fasting status will be recorded in study source documentation.

Urine samples will be obtained for urinalysis testing at visits specified in [Table 2](#) and [Table 4](#). The central laboratory will be responsible for performing a macroscopic urinalysis (urine dipstick) on the collected urine specimens. Specified abnormal macroscopic urinalyses defined as leukocytes, nitrite, protein, ketones, or blood greater than negative, or glucose greater than normal will be followed up with a microscopic analysis at the central laboratory.

For any laboratory test value outside the reference range that the Investigator considers to be clinically significant, the Investigator should apply the standard of care for medical evaluation and treatment per local guidelines:

- The Investigator will repeat the test to verify the out-of-range value at Investigator's discretion.
- The Investigator will follow the out-of-range value to a satisfactory clinical resolution.

A laboratory test value that requires a subject to be discontinued from the study drug or requires a subject to receive treatment will be recorded as an AE.

